Include a description of the availability of medical or psychological resources that subjects might require as a consequence of participating in this research and how referral will occur if necessary (e.g. availability of emergency medical care, psychological counseling, etc.)

Healthcare professionals will monitor the subject at all times during the operation. The patient will be reassured that although they are participating in the study, everything that happens during the case is already standard practice at UIHC for cardiothoracic surgery or interventional cardiology diagnostic procedures under general anesthesia. TEE probe maneuvering will only be done as necessary to minimize any physical trauma beyond what is already standard procedure in these patients. All patients will be given an identification number and be referred to by such. To prevent loss of confidentiality of the patient's medical information, we will keep all records used for this study in a locked office or on password protected computer system. Only members of the research team will have access to the records used in this study. No key will be kept as patients will not need to be contacted in the future.

- VIII.3** ***Does this study have a plan to have an individual or committee review combined data from all subjects on a periodic basis (such as summary or aggregate safety and/or efficacy data)?***

No

IX. Benefits

- IX.1** ***What are the direct benefits to the subject (do not include compensation or hypothesized results)?***

There are no direct benefits to the subject.

- IX.2** ***What are the potential benefits to society in terms of knowledge to be gained as a result of this project?***

This novel method to visually confirm epidural catheter placement and anesthetic spread within the epidural space could greatly increase the safety and success rate of epidural analgesia. Further, it provides an alternative to the ionizing radiation and contrast injection used in current methods of fluoroscopy to confirm catheter placement. By determining the success rate achieved using TEE as an alternative method to thread and confirm epidural catheter placement, it will allow us to compare with current techniques already in use and potentially improve patient safety and care.

X. Privacy & Confidentiality

X.1 *What are you doing to protect the privacy interests of the subjects?*

To protect patient privacy, researchers will be conducting the consent and study procedures in a private setting. Further, the research team will only be collecting the information necessary to complete the study.

X.2 *Are you collecting the Social Security Number of any subjects for any purpose?*

No

X.4 *How will information/data be collected and stored for this study (check all that apply):*

Paper/hard copy records (hard copy surveys, questionnaires, case report forms, pictures, etc.) - Paper/hard copy records, including consent documents and any other material printed for the study, will be stored in the primary investigator's office in a locked file cabinet. Further, patients will be assigned a unique identification number. They will always be referred to by this number. The patient's hospital number and day of surgery will be recorded, but will not be disclosed to anyone outside the research team. We will record the hospital number only to access the patients' chart later if needed. The database that contains the identifiers will be password protected so that the only the investigators needing it can access it. No unnecessary patient identifiers will be recorded, and those that are needed will be deleted at the earliest possible time. Only data necessary to collect for the study will be recorded.

Electronic records (computer files, electronic databases, etc.) - Electronic records will be kept on the password protected Anesthesia department server. The members of the research team will be the only people with access to the files. No records will be kept on personal computers. Further, patients will be assigned a unique identification number. They will always be referred to by this number. The patient's hospital number and day of surgery will be recorded, but will not be disclosed to anyone outside the research team. We will record the hospital number only to access the patients' chart later if needed. The database that contains the identifiers will be password protected so that the only the investigators needing it can access it. No unnecessary patient identifiers will be recorded, and those that are needed will be deleted at the earliest possible time. Only data necessary

to collect for the study will be recorded.

Name -

Title - System Administrator and System Programmer II

University Job Classification - IT Security Officer

X.5 ***Do the confidentiality protections indicated above allow only members of the research team to access the data/specimens?***

Yes

X.7 ***Does your study meet the NIH criteria for a [Certificate of Confidentiality](#) or will you be applying for Certificate of Confidentiality?***

No

XI. Data Analysis

XI.1 ***Describe the analysis methods you will use, including, if applicable, the variables you will analyze***

We are planning to determine the success rate achieved using TEE guidance to thread an epidural catheter to a targeted thoracic spinal level. Post-operative radiograph will be used to confirm catheter position for comparison. Thus, we will only use exploratory descriptive statistics for analysis.

XI.2 ***Provide the rationale or power analysis to support the number of subjects proposed to complete this study.***

Because this is a novel technique, we have no base for the ability to use TEE to guide and confirm thoracic epidural catheters. We assume that twenty pediatric patients will provide adequate power to confirm a high success rate for this novel technique in both imaging and guiding the catheter. Therefore, total of 25 subjects will be needed due to account for subjects who may withdraw or become ineligible.

XII. Future Research

XII.1 ***Do you wish to keep any information about subjects involved with this research project so that members of the current research team may contact them in the future for your own research projects?***

No

XII.2 ***Do you wish to keep any information about subjects involved with this research project so that [other researchers](#) may contact them for future research?***

No

XII.4 ***Does this project involve storing any data, tissues or specimens for future research?***

Yes – contribution for future use is mandatory for participation in the study

ROC. Record of Consent

ROC.1 ***Select which option applies to address the University of Iowa Health Care policy [IM-MR-06.21](#) titled "[Documentation of patient participation as a subject in a research protocol or use of an investigational medication,](#)***

study medication, investigational device, or biologic.”

The research related activities proposed in this study **does meet** the registration requirements under the University of Iowa Health Care policy IM-MR-06.21 titled “Documentation of patient participation as a subject in a research protocol or use of an investigational medication, study medication, investigational device, or biologic.” **The below information must be completed and approved as part of the IRB application. This information contained within this page will be used to create the Epic Research Study Application Form.**

ROC.2 ***Select a publicly viewable title for this study. (This title will be visible in EPIC)***

Release full title

ROC.3 ***Select research team member who has taken Epic Training***

ROC.4 ***Who is a 24/7 contact person for projects involving treatment(s) or procedures that result in complications or side effects?***

[name]

Other contact information that may be relevant to a subject’s clinical care (i.e. may be important if the contact person is not available 24/7 or an alternate contact may be required.)

ROC.5 ***Describe the key complications from the study drug(s) listed below or study procedure(s):***

The patient might experience sore throat from TEE manipulation for a few hours after the surgery.

ROC.6 ***Any other information that may be important to emergency personnel:***

None

XIII. Other Mod and/or Comments

XIII.1 ***Most modifications should be made in the appropriate section (see Index) of the project itself. If you need to describe other changes, or wish to add comments about something you changed, please do so here.***

CR I. Project Summary

CR I.1 ***Summarize your progress to date in conducting the study at Iowa. Address each of the bulleted items below in your response.***

Describe any problems or delays

Describe any significant changes to the study design (previously approved by the IRB) since the study began (requests for new changes should be described on a Modification form)

Describe any significant subject experiences (benefits, adverse events/adverse reactions) since the last IRB review.

No problems or delays in the study. No changes were made since the study began. No significant subject experiences noted since the last IRB review.

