Transesophageal echocardiography (TEE) to guide and confirm epidural catheters in pediatric patients

NCT Number: 02415998

[name]

Document Date: July 12, 2012

Transesophageal echocardiography (TEE) to guide and confirm epidural catheters in pediatric patients

PI: [name]

IRB ID #: 201207769

Form Content

I. Project Introduction

I.1 Project to be reviewed by:

IRB-01

I.2 Project Title:

Transesophageal echocardiography (TEE) to guide and confirm epidural catheters in pediatric patients

I.3 Short Title (optional):

I.4 Provide a short summary of the purpose and procedures of the study proposed in this IRB application.

DO NOT include information on studies not proposed in this application.

Use LAY terminology only. This must be easily understandable by IRB community members and nonscientists.

DO NOT cut and paste technical abstracts from funding applications that may not be understood by a general audience.

The aim of this study is to assess whether transesophageal echocardiography (TEE) can be used to successfully guide an epidural catheter to a targeted thoracic level in pediatric patients. The catheter will be placed in the epidural space under real-time TEE imaging and assistance by a trained TEE operator (this could include an anesthesiologist or cardiologist).

I.5 Specify your research question(s), study aims or hypotheses (do not indicate "see protocol")

The primary outcome is to determine the success rate achieved using TEE guidance to thread an epidural catheter to a targeted thoracic spinal level. Post-operative radiograph will be used to confirm catheter position.

The secondary outcomes include analysis of catheter tip position within the epidural space as anterior, lateral or inferior to the spinal cord. Further, efficacy of the catheter will be determined using the following criteria from previous studies [1]: Hemodynamic response at skin incision analyzed by heart rate and systemic blood pressure changes using the no change in HR or BP or changes < 20% from baseline were considered "sufficient block" to surgical stimulation, while HR or BP changes > 20% from baseline were considered "not sufficient block" to surgical stimulation.

I.6 Background and significance and/or Preliminary studies related to this project. (do not indicate "see protocol")

Epidural block has been utilized extensively in pediatric patients [2], however, blind advancement of epidural catheters to the thoracic space can be technically

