degree toward the descending aorta, with adjusted gain and depth in order to obtain the best image of the spinal cord and epidural space possible. A trained TEE operator (either an anesthesiologist or cardiologist) will control the machine and obtain an image of the spinal canal at the targeted vertebral level. They will then capture an image of the spinal canal at this level. A different anesthesiologist will begin placement of a thoracic epidural catheter, as is standard protocol for anesthesia, however, these catheters are normally threaded blindly. In our study, catheter placement will occur with the assistance of the TEE operator to confirm the catheter is advanced to target level. The real-time TEE image generated will allow for confirmation of the catheter within the epidural space at this point. Further, when the anesthesiologist believes they have reached the targeted thoracic level, they will inject 1 mL of normal saline to assess intrathecal spread in the epidural space. When the catheter is threaded to sufficient targeted level, as determined by the anesthesiologist, a bolus dosage of anesthetic will be given (0.4 mL/kg of 1.5% Lidocaine) again, this is all standard procedure in these surgeries. Because it is standard procedure for epidural catheter to be placed blindly prior to surgery, we hope to determine whether the use of TEE for guidance and confirmation will actually improve the results and decrease the time needed to ensure adequate placement. Anesthesiologists will be given three attempts to use TEE for confirmation. The anesthesiologist will be able to see the image on TEE, and the trained TEE monitor will be allowed to discuss images seen on the ultrasound screen.

At this time, the trained TEE operator will assess the location of the epidural catheter within the epidural space at target level on real-time TEE images as anterior, posterior or lateral to the spinal cord. Further, the TEE operator will take images of the catheter confirmed at the target spinal level in order to later compare with the images taken prior to catheter threading.

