At this point, the TEE probe will be returned to midesophageal level to visualize the heart and the operation will proceed as usual. Because this study will occur while the patient is being prepared for surgery by the anesthesia team as usual in these surgeries, no additional time in the operating room or catheter laboratory will be required. In fact, it is possible that TEE guidance could decrease time spent under anesthesia and improve confidence in the catheter position. During the procedure, at the time of surgical incision, the anesthesiologist will be asked to note whether the patient exhibits a hemodynamic response to incision. This will be determined by the criteria used in previous studies (Willschke 2006) analyzed by heart rate and systemic blood pressure changes using no change in HR or BP or changes < 20% from baseline were considered "sufficient block" to surgical stimulation, while HR or BP changes > 20% from baseline were considered "not sufficient block" to surgical stimulation. These changes will correlate with the efficacy of the epidural block.

Following surgery, a post-operative x-ray will be taken as is standard procedure to visualize the heart. Because this study will occur only in pediatric patients, the x-ray will also capture and exhibit catheter placement around the spinal cord. This is currently the gold standard confirmatory technique for epidural catheters and this will be used to compare with the success of pre-operative TEE guided catheter placement.

Following all procedures, the success rate achieved by TEE in threading a catheter to the epidural space of targeted spinal levels as compared to confirmation by post-operative x-ray. Further the efficacy of that catheter will be determined with correlation to catheter position (anterior, lateral or posterior to the spinal cord). When looking at patient medical records, we will only collect the following data: height, weight, age, any known history of esophageal abnormalities, lesions or disease, current procedure, hemodynamic markers, FLACC score immediately after surgery when the patient is in the post-anesthesia care unit ** or pediatric intensive care unit ** postoperatively 24 hours after surgery and total morphine used within 24 hours after surgery.

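### The secondary block-efficacy outcome is noted at incision by an anaesthesiologist who may know the TEE result, with baseline and window undefined; masked scoring from timed values would be a cheap improvement

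*Combined protocol and SAP*

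**What the plan says.** Section I.5 makes block efficacy a secondary outcome: "efficacy of the catheter will be determined using the following criteria from previous studies". The criterion, repeated in VII.E.6, is a change in heart rate or systemic blood pressure at skin incision. Less than 20% from baseline is a sufficient block and more than 20% is not.

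VII.E.6 says how the outcome is obtained. At incision, "the anesthesiologist will be asked to note whether the patient exhibits a hemodynamic response to incision".

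Earlier in VII.E.6 the roles at catheter placement are set out. One clinician runs the TEE probe. "A different anesthesiologist will begin placement of a thoracic epidural catheter", and this person decides when the target level has been reached. On access to the images: "The anesthesiologist will be able to see the image on TEE, and the trained TEE monitor will be allowed to discuss images seen". The TEE operator classifies the catheter's position relative to the cord before surgery proceeds.

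The use of the outcome is stated later in VII.E.6: "the efficacy of that catheter will be determined with correlation to catheter position (anterior, lateral or posterior to the spinal cord"). Section VII.B.37 adds an interest in the sensitivity and specificity of TEE confirmation in relation to catheter efficacy.

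The data taken from the record form a closed list: "When looking at patient medical records, we will only collect the following data: height, weight, age", continuing with, among other items, "current procedure, hemodynamic markers, FLACC score immediately after surgery". Section XI.1 limits the analysis to descriptive statistics. Sections VI.15 and XI.2 give 20 children with data, and VI.13 and XI.2 give 25 enrolled.

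**The concern.** The study relates two measurements to each other: what TEE showed, and whether the block worked. For that comparison to be informative, the second should be recorded without knowledge of the first. Here the second is noted in the operating room, after the TEE reading, by someone whom nothing in the plan keeps from knowing that reading.

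A numeric cut normally limits this kind of influence. It does so less when the scorer must also settle which value is the baseline and how long after incision to look, since a response close to 20% can then fall on either side. There is no control arm (VI.13), so nothing within the study would show that this had happened, and a descriptive analysis does not remove bias from the rate it describes.

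**Working it through.** **Who scores, and what that person can know.** The plan states no figure for this, so the check is of the text.

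1. VII.E.6 separates the TEE operator from the anaesthesiologist who places the catheter.
2. The placing anaesthesiologist may see and discuss the TEE image.
3. The operator reads the tip position before incision.
4. At incision the scorer is simply the anaesthesiologist. No other person is introduced, and no section provides masking, an independent assessor or later scoring from the record.

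So the scorer can know the TEE result. The text does not say outright that the scorer is the person who placed the catheter.

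**How much discretion the rule leaves.** The cut is fixed at 20%. The baseline time and the post-incision window are not given, and a change of exactly 20% falls in neither class.

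**Effect per case.** Input: 20 evaluable children (VI.15, XI.2).

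- One reclassified case: 1/20 = 5 percentage points.
- Three cases: 3/20 = 15 points, for example 14/20 = 70% against 17/20 = 85%.
- Exact (Clopper-Pearson) 95% intervals: 14/20 gives 45.7% to 88.1%; 17/20 gives 62.1% to 96.8%.

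The intervals overlap widely, so a three-case shift lies within sampling error. An interval does not allow for a systematic tilt, however.

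**Illustration with assumed inputs.** Let p be the true sufficient-block rate and m the share of insufficient blocks noted as sufficient, with no errors the other way. Then observed rate = p + (1 − p) × m. The documents give neither p nor m.

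| p (assumed) | m = 10% | m = 25% | m = 50% |
|---|---|---|---|
| 70% | 0.70 + 0.30 × 0.10 = 73% | 0.70 + 0.30 × 0.25 = 77.5% | 0.70 + 0.30 × 0.50 = 85% |
| 80% | 0.80 + 0.20 × 0.10 = 82% | 0.80 + 0.20 × 0.25 = 85% | 0.80 + 0.20 × 0.50 = 90% |

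Over this range the rate is inflated by 2 to 15 points. This shows sensitivity only and does not estimate the bias that would occur.

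**Whether the data for masked scoring are there.** The closed list in VII.E.6 names haemodynamic markers without saying which values or at what times, and it does not contain the time of incision. Masked scoring therefore needs additions to that list.

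**The case against.** The strongest reply is that the outcome is secondary and has an objective threshold, in a single-arm study that promises only descriptive statistics, while the primary outcome rests on the radiograph. All of that is correct, and it limits the severity. The text can also be read as allowing classification from recorded values, because haemodynamic markers are taken from the chart. That reading is possible, but the plan does not say so. It asks the anaesthesiologist to note the response and leaves the baseline and window open.

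A reader might infer several stronger points that the documents do not support:

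- *The values needed for masked scoring are already collected.* Only unspecified haemodynamic markers are listed, without incision time.
- *The scorer controls the background anaesthetic and could suppress a response.* This may be a natural assumption about the role, but no section says it, and masked scoring would not correct it, because the recorded values would already carry any such effect.
- *The incision response is the study's only evidence on block quality.* VII.E.6 also collects FLACC scores and 24-hour morphine use. The incision response is the only stated efficacy criterion, which is a narrower claim.
- *The comparison across tip positions is shown to be biased.* The plan states no expectation that one position gives a better block, so no direction follows. A general tilt towards sufficient would raise the overall rate without necessarily favouring any position.

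**Conclusion.** The point holds as a minor one. The stated efficacy outcome can be scored by someone who knows the TEE result, under a rule whose baseline and window are open. This could bias the descriptive efficacy rate, and it means the efficacy call is not assured to be independent of the TEE reading with which it is compared.

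The size per case is 5 percentage points at 20 evaluable children. The total is unknown, because the documents give no basis for how many responses will fall near 20% or how often knowledge of TEE would sway the call. The conclusion rests on reading the plan's silence as allowing an unmasked scorer. It does not require that the scorer and the placing anaesthesiologist be the same person, and it does not show that bias will occur. The primary outcome is untouched.

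**What to change.** In VII.E.6:

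1. Have the anaesthesiologist mark only the time of incision, in place of noting whether there was a response.
2. Add to the data list the incision time, and heart rate and systemic blood pressure at prespecified times before incision (a defined baseline) and after it (a defined window).
3. Have an existing team member who handles data, and who has no access to the TEE images or the tip-position entry, apply the existing 20% rule. Section VII.D.5 already refers to team members who enter or analyse data; the masking of one of them would have to be arranged.
4. State in advance which class a change of exactly 20% belongs to.

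The cost is a small extension of the closed data list and extraction time for 20 to 25 records. No visit, procedure or patient is added and clinical care is unchanged. The change removes bias in recording the outcome. It does not remove any effect of anaesthetic management on heart rate or blood pressure, and the report should say so.

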VI.9 *What is the percentage of minor male subjects?*

50

VI.10 *What is the percentage of minor female subjects?*

50

VI.11 *Will any of the minors enrolled be in foster care or Wards of the court?*

No

VI.13 *Describe EACH of your subject populations
Include description of any control group(s)
Specify the Inclusion/Exclusion criteria for EACH group*

The study population will include 25 pediatric patients scheduled to undergo cardiothoracic surgery or interventional cardiology diagnostic procedures under general anesthesia. All subjects will also be scheduled to undergo post-operative chest x-ray as a routine part of their clinical care, so no additional exposure to ionizing radiation will occur due to this study. We will exclude any patients with known esophageal abnormalities, lesions or disease that would disqualify the patient for the use of TEE as standard procedure. We will further exclude any patients that are solely undergoing TEE diagnostic procedures and only include patients that are already scheduled to undergo procedures where TEE is used as part of routine surgical preparation. There is no control population needed because all patients will receive the same treatment, three attempts at TEE guided catheter placement.

VI.14 *Provide an estimate of the total number of subjects that would be eligible for*

inclusion in each of your study populations (include your control population if applicable)

25 pediatric patients. There is no control population needed. We expect to complete this study in one year.

VI.15 ***Describe how you will have access to each of your study populations in sufficient number to meet your recruitment goals.***

Outpatient pediatric cardiac surgery patients will be recruited at the pediatric cardiology clinic when patients visit for the preoperative evaluation. Inpatient cardiac patients will be identified initially by using the EPIC operating room schedule on the day before surgery. We will have access to these populations by working within the Department of Anesthesiology and by monitoring the OR schedule for patients scheduled to undergo cardiothoracic or interventional cardiac diagnosis or surgery. The use of TEE and post operative x-ray are already standard procedure for each of these cases. A trained TEE operator (anesthesiologist or cardiologist) will be available to control the TEE probe and assist in catheter guidance. Patients will be recruited until data has been collected in 20 pediatric patients.

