TEE is routinely used in cardiothoracic and interventional surgeries as well as in detecting thromboses, valvular defects and congenital heart disease. TEE is used nearly universally in cardiac surgical operating rooms and exhibits a low risk of complications (Daniel 1991). While it has been shown that TEE can be used to visualize the spinal column when attempted (Chitilian 2006), TEE has never been used to confirm the placement of epidural catheters using this new window of view. Because epidural catheters are usually blindly threaded, we would like to assess the sensitivity and specificity achieved by TEE in correlating confirmation of an epidural catheter at targeted thoracic spinal levels and the efficacy of that catheter.

VII.C. Project Description (C)

VII.C.1 *Does this project involve any [research on genes or genetic testing/research?](#)*

No

VII.D. Project Description (D)

VII.D.1 *Check all materials/methods that will be used in recruiting subjects (you will need to attach copies of all materials at the end of the application):*

Use of any information available to the researchers or their colleagues because this person is a patient OR use of any information considered to be Protected Health Information (PHI) OR review of patient/clinic records - Operating room schedule

Referral from colleague - Thoracic surgery physicians and nurses may identify potential patients. Also, some patients may be identified by Pre-Anesthesia Evaluation Clinic staff.

VII.D.2 *List the individual data elements you will need to access/use from the patient or clinic records to identify potential subjects for recruitment*

We will need to access patient records to check the patient's eligibility for the study by checking their surgical procedure, past medical history, counter indications for TEE use intra-operatively (esophageal trauma, lesion or disease) and age.

VII.D.3 *Describe why you could not practicably recruit subjects without access to and use of the information described above*

Many patients may be unaware that they are eligible for the study because they do not understand the routine use of TEE in the operating room. They

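### Does the plan score its primary success rate by two conflicting rules, one judged under TEE and one confirmed on the film?

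*Combined protocol and SAP*

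**What the plan says.** Section I.5 defines the primary outcome as the success rate of threading to a targeted thoracic level under TEE guidance and continues: "Post-operative radiograph will be used to confirm catheter position".

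Section VII.E.6 describes placement with the TEE operator's help, allows three attempts, and calls the post-operative film the current gold standard. It then says "this will be used to compare with the success of pre-operative TEE guided catheter placement", and later sets the TEE success rate "as compared to confirmation by post-operative x-ray".

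Section XI.1 repeats the aim in I.5 and adds: "Post-operative radiograph will be used to confirm catheter position for comparison". It limits the analysis to descriptive statistics.

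Section VII.B.37, which answers a question about how the study use differs from the approved use of the device, says "we would like to assess the sensitivity and specificity achieved by TEE in correlating confirmation of an epidural catheter at targeted thoracic spinal levels". The sentence then goes on to the efficacy of the catheter.

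On numbers, VI.15 states: "Patients will be recruited until data has been collected in 20 pediatric patients". Section XI.2 says a "total of 25 subjects will be needed due to account for subjects who may withdraw or become ineligible". Section IX.2 says of the success rate that "it will allow us to compare with current techniques already in use".

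**The concern.** The film seems to play two parts. If it confirms position, the film decides success. If it is compared with a success already reached under TEE, TEE decides success and the film only comments on it. A catheter at target on TEE but off target on the film would then fail under one rule and pass under the other. XI.1, which ought to settle this, uses both words. VII.B.37 adds sensitivity and specificity, for which XI.1 plans no analysis. No section names the denominator.

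The stake is real in principle. Because the analysis is descriptive, this one proportion is the main result, and the investigators mean to set it beside existing techniques. A rate judged by TEE alone could not expose TEE's own misreadings.

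**Working it through.** **1. The plan's own numbers.** The target is 20 children with data and 25 enrolled, so 25 − 20 = 5 spare places. This matches 20 / (1 − 0.20) = 25, but the 20% loss is back-solved; XI.2 states no rate. The 20 itself cannot be reproduced, because no null rate, target rate, power or precision is given.

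**2. The sections side by side.**
- I.5: the film confirms position.
- VII.E.6: the film is the gold standard, and the TEE placement is compared with it.
- XI.1: the film confirms position, for comparison.

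Comparing a placement with its gold standard is the usual way of verifying it, so the three statements are compatible. VII.E.6 does leave it to the anesthesiologist to decide during the procedure that the level has been reached, but that sentence governs when the anesthetic bolus is given. It does not define the outcome.

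**3. Size of the scoring choice.** All counts here are assumptions, since the documents give no disagreement rate. Take 20 children: a = 16 at target on both, b = 2 at target on TEE only, c = 0 at target on film only, d = 2 off target on both. Intervals are exact (Clopper-Pearson) 95%.
- Film-confirmed: (a + c)/20 = 16/20 = 80.0% (56.3 to 94.3).
- TEE-judged: (a + b)/20 = 18/20 = 90.0% (68.3 to 98.8).
- Difference: (b − c)/20 = 2/20 = 10.0 points, or 1/20 = 5.0 points per discordant child.
- One discordant child (a = 17, b = 1): 17/20 = 85.0% (62.1 to 96.8) against 90.0%.
- No discordant child: the rates are equal.

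**4. Denominator.** Suppose a technique failure were left out and replaced, so that s successes were reported over 20 instead of 21. The rate would rise by s/20 − s/21 = s/420: 10/420 = 2.4 points at s = 10, and 20/420 = 4.8 points at s = 20. The documents do not point that way. VI.13 gives every child three attempts, and XI.2 reserves the spare places for withdrawal or ineligibility. A child whose catheter never reaches the target has data, namely a failure. Dividing by all 25 (16/25 = 64.0%) would count the spare places as failures, which no section supports.

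**5. Sensitivity and specificity.** With the film as reference, the counts in step 3 give sensitivity 16/16 = 100% (79.4 to 100) and specificity 2/4 = 50.0% (6.8 to 93.2). VII.B.37 does not name the film, however, and its sentence may intend block efficacy as the comparator. In either case these are different measures from the success rate, not another way of scoring it.

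**The case for a change.** The strongest case for a change is that XI.1 is where the rule belongs, and the rule is not there. It is silent on TEE-film disagreement, three failed attempts, no usable TEE image and an unreadable film. No section says how close to the intended level counts as at target. Read literally, VII.E.6 does speak of a success that precedes the film. The choice could also colour the result. The background in I.6 cites failure as high as 32% from caudal levels in one study, or 100 − 32 = 68% success. On the assumed counts the TEE-judged lower limit of 68.3% just clears that figure, while the film-confirmed interval from 56.3% includes it.

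The silence stands, but the consequence does not follow. XI.1 plans neither an interval nor a test against 68%, and the contrast depends on choosing two discordant children. Nor is every disagreement a TEE error: TEE is read before surgery and the film is taken afterwards, and the documents do not say that the catheter stays put in between. Counting such a child as a non-success is the cautious choice, and it is the one the film-confirmed reading makes.

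**Conclusion.** The concern does not call for a change. The wording varies between confirming and comparing, but the sections share one reading: success per child, verified on the post-operative film, with technique failures counted as non-successes. An analyst following that reading reports a sound descriptive rate. Both the TEE images and the film are collected in any case, so agreement between them can be described without altering the study.

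The difference between the two scoring rules would be 5.0 points per discordant child in 20, and zero if TEE and film agree. The possible 2.4 to 4.8 points from the denominator rest on a practice the plan does not suggest. The conclusion assumes that failures are kept in the count and that the film's gold-standard role in VII.E.6 governs the outcome. What is left is missing detail in a small, single-arm, descriptive study.
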